7.2 Baseline

Participants will complete the baseline questionnaire (including EHP-30 + Section C and EQ-5D-5L) prior to randomisation.

The site research team will complete the baseline CRF including information on parity; age, ethnicity, current and previous treatments used for endometriosis associated pain.

At baseline, we will also collect contact details of participants (including postal address, email, home and mobile number) and their contact preferences (see section 7.4) along with details of their GP.

7.3 Surgery

The site research team will complete a surgical CRF for any participants undergoing surgery. This will include those randomised to surgery who have surgery, and those randomised to medical management who go on to have surgery.

7.4 Follow-up

Patient reported outcomes will be collected at 12 weeks, 12 months and 18 months post-randomisation using questionnaires completed by women at home. The questionnaires will include EHP-30 + Section C, EQ-5D-5L, symptoms, and questions about current and recent treatment (including analgesic use), satisfaction with treatment, serious adverse events/complications, and any pregnancy.

While the chances of pregnancy are very low (based on our eligibility criteria), we will collect and analyse data on women who become pregnant during the follow up period.

At baseline, participants will be asked for their contact preferences for questionnaires. Those selecting email as their preference will have a link to the questionnaire emailed to them. Those selecting post as their preference will have the questionnaire posted to them. Those selecting text messaging as their preference will have a link to the questionnaire texted to them. First reminders will be emailed, posted or texted to participants (according to their stated preference). A second reminder (by telephone) will be attempted but if there is no response by telephone, a final postal reminder will be sent.

Questionnaires will be administered to all women who were randomised in the study, regardless of their compliance to the randomised treatment unless they have opted out of questionnaire follow-up. This means that patients who have not received their allocated treatment, have received the non-randomised treatment or have discontinued medical management will continue to be followed up in the study.

If questionnaires are returned as non-deliverable, attempts will be made by site staff or staff at the Trial Office to trace the participant.

7.5 Capture of data from medical records

The secondary care medical notes of all participants will be reviewed at 18 months after randomisation and any relevant data on further treatment (and outcome of pregnancy, where relevant) will be captured. The prescription record for each participant will also be requested directly from GP practices or by linking to patient prescribing data (e.g. NHS Digital Data Access Request Service (<https://digital.nhs.uk/data-and-information/data-insights-and-statistics/prescribing-and-medicines-team>, www.nhsresearchscotland.org.uk/research-in-scotland/data/health-informatics, in Scotland, or equivalent) to accurately establish medicinal use during the trial .

7.6 Change of Status/Withdrawal procedures

Participants remain in the trial unless they choose to withdraw consent. Participants are free to withdraw from the trial at any timepoint. All changes in status with the exception of complete withdrawal of consent means the participant is still followed up for all trial outcomes wherever possible. All data collected up to the point of complete withdrawal is retained and used in the analysis.

Following informed consent, if a participant loses capacity, the consent given when capable remains legally valid. In such circumstances, a decision needs to be made, in conjunction with the participant and any family or carers, in relation to ongoing participation in the study.

Participants who do not receive their allocated treatment, receive the non-randomised treatment or discontinue their medical management are not considered withdrawals and will be followed up for all trial outcomes unless they request otherwise. One of the outcomes is treatment received. This is a pragmatic study and will monitor accruing data on treatment initiated and continued during the study which will inform the proportion of participants continuing in the two randomised treatment pathways.

Participants who request that no further questionnaires are issued (i.e. completing questionnaires) will be followed up for other trial outcomes unless they are complete withdrawals.

Participants for whom any outcome data are available are included in an intention to treat analysis.

7.7 Data processing

Research nurses will enter locally collected data in the centres into the study website. Staff in the Trial office will work closely with site Research Nurses to ensure the data are as complete and accurate as possible. Postal questionnaires will be entered into the study website by trial office staff.

7.8 Long term follow-up

We plan to seek funding to follow-up participants in the long-term using data from NHS and other government central registries, and GP and hospital notes. We will seek informed consent for this at the outset of the trial.

8. Safety

The DIAMOND trial involves two different policies for treating deep endometriosis: medical management or surgical management (with or without adjuvant medical treatment). The MHRA has confirmed that DIAMOND is not a CTIMP and therefore the safety reporting within DIAMOND will follow guidance for safety reporting in research other than CTIMPs.

Medical management will involve hormonal treatment for 18 months. The choice of hormonal medication will be at the discretion of the treating clinician in discussion with the participating woman (in line with current accepted UK prescribing practice), avoiding any treatment which has either failed or caused unacceptable side effects in the past. Surgical management (laparoscopic ablation or excision of endometriosis/endometrioma) is well established in current NHS clinical practice. Women in both trial arms can receive additional neuromodulator drugs, analgesics and other interventions for pain relief, as required.

Adverse events (AEs) in DIAMOND may occur during or after any type of surgery for endometriosis or may be related to the use of hormonal treatment or may be related to other treatment for endometriosis.

At each follow-up questionnaire, we will ask women about serious adverse events and complications and these will be reported as a secondary outcome. Women may not be able to distinguish between serious adverse events/complications that occur as a result of their hormonal treatment from those that occur from other treatment and therefore we will ask about side effects as a result of treatment for endometriosis. Those meeting the criteria for serious will be reported as SAEs through the safety reporting process within the study.

8.1 Definitions

Term	Definition
Adverse Event (AE)	Any untoward medical event affecting a clinical trial participant.
Serious Adverse Event (SAE)	Where an AE 
• results in death;• is life threatening (i.e. the subject was at risk of death at the time of the event; it does not refer to an event which hypothetically might have caused death if it were more severe);• requires overnight hospitalisation or prolongation of existing hospitalisation;• results in persistent or significant disability or incapacity;• is a congenital anomaly or birth defect,• is otherwise considered medically significant by the investigator

Adverse events are **not**:

- continuous and persistent disease or symptom, present before the trial, which fails to progress;
- signs or symptoms of the disease being studied; or
- treatment failure (persistent pain).

In this trial, all serious and related AEs will be recorded as SAEs (see definition of “related” in section 8.3.2 below).

Hospitalisations for treatment planned prior to randomisation and hospitalisation for elective treatment of a pre-existing condition will not be considered as a SAE within DIAMOND. Complications occurring during such hospitalisation will also not be considered, recorded or reported as a SAE – unless there is a possibility that the complication arose because of the study interventions.

Planned overnight admission following endometriosis surgery (for example because of social circumstances) is not considered a SAE. Hospital visits (planned or unplanned) associated with further interventions due to endometriosis (e.g. further surgery) will be recorded as an outcome measure but will not be reported as SAEs.

Complications occurring during endometriosis surgery will be considered, recorded and reported as a SAE, if appropriate.

Any SAEs related to the participants’ endometriosis treatment that are not further interventions (e.g. if a participant is admitted to hospital for treatment of infection) will be recorded and reported as a SAE.

Admissions for non-elective procedures or emergency procedures for any condition will be considered, recorded and reported as a SAE.

All deaths for any cause (related or otherwise during the follow up period of 18 months) will be recorded on the serious adverse event form.

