In a recent survey of 66 women with endometriosis undertaken by the applicants in conjunction with Endometriosis UK, 47% of responders stated that they were willing to be randomised to either medical or surgical treatment and most (74%) felt that relief of pain and quality of life were the most important outcomes. The best time point for the assessment of symptoms was felt to be 6, 12 or 24 months after starting treatment by 42%, 35% and 17% women respectively, while 6% felt that outcomes should be assessed at several points in time.

Of 79 specialist clinicians surveyed by the British Society for Gynaecological Endoscopy, 43% felt there was insufficient evidence to inform decision making in DE management and 94% were willing to randomise their patients to either a surgical or medical pathway. Most (64%) considered both pain and quality of life to be the most important outcome measures; with 3% prioritising pain and 34% quality of life. Post treatment, the optimal follow-up period was felt to be 12 and 24 months by 44% and 36% respectively, while 20% of respondents favoured measurements at multiple time points.

The current clinical pathway for management of women with pain due to DE involves initial medical management using a variety of hormonal agents, but ultimately many women go on to have surgery. Laparoscopic excision of endometriosis has been shown to improve pain symptoms in DE¹³ and surgery has been the traditional approach favoured by many clinicians who believe that medical treatment cannot reverse pelvic scarring caused by the condition.¹⁴⁻¹⁶ While surgery is the only option in women with mechanical obstruction of the bowel or ureters, long-term hormonal treatment with the aim of shrinking areas of endometriosis have been

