4.3 Inclusion and exclusion criteria

Inclusion criteria:

- Women aged 18–49 years old seeking treatment for pain
- Confirmed deep endometriosis (laparoscopic or other routinely used investigative radiology technique)
- Suitable for either medical or surgical management
- Able and willing to give informed consent to participate and to participate in study procedures (*There are provisions within the protocol for recording consent from patients who are not able to read or write (but who have capacity and who can speak English sufficiently to understand the information being provided orally); see section 4.7*)

Exclusion criteria:

- Unfit for laparoscopic surgery
- Have used or currently using GnRH analogues without satisfactory relief of pain symptoms
- Previous bilateral oophorectomy
- Previous surgery for deep endometriosis
- Actively trying to conceive
- Confirmed bowel stenosis
- Hydronephrosis or hydroureter caused by ureteric stenosis
- Endometrioma > 5cm in diameter
- Women with preference for hormonal medical or surgical treatment
- Current pregnancy or breast feeding

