8.3.2 Evaluating AEs

When a potential SAE is reported in a questionnaire, it is the responsibility of the Site Principal Investigator (or delegate) to review appropriate documentation (e.g. hospital notes, laboratory and diagnostic reports) related to the adverse event.

Assessment of Seriousness

The Investigator should assess seriousness as defined in Section 8.1.

Assessment of Relatedness (causality)

The Investigator will make an assessment of whether the SAE is likely to be related to research procedures according to the following definitions:

- **Related:** resulted from administration of any of the research procedures required by the protocol, whether or not it is either a) the specific intervention under investigation or b) it is administered outside the study as part of normal care.
- **Unrelated:** where an event is not considered to have resulted from any of the research procedures.

Alternative causes such as natural history of the underlying disease, concomitant therapy, other risk factors and the temporal relationship of the event to the treatment are considered.

Assessment of Expectedness

Expectedness will be assessed for events that meet the criteria for serious outlined in Section 8.1.

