Those randomised to surgical intervention, will receive their surgery in line with local procedures during the pandemic. The pandemic may result in some delays to the waiting list if restrictions are in place. In saying that, grade 4 endometriosis is a category 1 priority due to level of symptoms and risk to bowel and renal tract. As such, advanced endometriosis surgical lists in endometriosis centres are all running at normal pre-covid levels. The research nurse will monitor the surgical lists to identify when surgery has been booked; and thereafter to confirm that surgery has taken place. The participant will be asked to use their usual contraception or barrier contraception until their operation and a pregnancy test will be performed as part of routine care prior to the procedure. If the woman is already taking hormonal treatment to suppress endometriosis symptoms, they will be advised to continue using this until their surgery. For pragmatic reasons, any changes to medical treatment used prior to surgery will be accepted, in line with NICE guidelines⁷.

Follow up

Follow up will continue to be managed remotely as outlined in the main protocol, in line with current guidelines.

Qualitative component

It is anticipated that the qualitative component will be completed remotely; if and when current restrictions on social distancing are lifted, face to face activity may commence.

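### Section 8.1 gives conflicting rules for new bowel or ureteric obstruction from endometriosis, so the same event may or may not reach the SAE comparison

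*Protocol*

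**What the plan says.** **Definition of an AE (8.1).** The definition is broad: "Any untoward medical event affecting a clinical trial participant". Two of the listed exclusions bear on this point. One removes "continuous and persistent disease or symptom, present before the trial, which fails to progress". The next removes "signs or symptoms of the disease being studied", with no exception for new organ complications.

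**Definition of an SAE (8.1).** Events are recorded as SAEs when they are serious and related. Hospital visits for further endometriosis interventions, whether or not they were planned, "will be recorded as an outcome measure but will not be reported as SAEs". A later sentence in the same section makes any admission for a non-elective or emergency procedure an SAE, whatever the condition. All deaths are recorded.

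**Relatedness and reporting (8.3.2, 8.3.3, 8.3.5).** A related event is one that results from a research procedure. In judging this, "Alternative causes such as natural history of the underlying disease" are considered. Section 8.3.3 says that serious but unrelated events go in summary to the DMC. Section 8.3.5 speaks only of related SAEs going to it.

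**Why obstruction matters here.** Confirmed bowel stenosis and "Hydronephrosis or hydroureter caused by ureteric stenosis" are exclusions (4.3). The Background says that "surgery is the only option in women with mechanical obstruction of the bowel or ureters". Appendix 3 explains surgical priority by saying that "grade 4 endometriosis is a category 1 priority due to level of symptoms and risk to bowel and renal tract".

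**The concern.** The trial leaves deep disease in place in one arm for up to 18 months and plans to remove it early in the other. Harms of operating have a dedicated CRF and a long list of expected complications in 8.2.2. A natural counterpart is a woman whose bowel or ureter becomes narrowed by disease that has not been removed. Because women with bowel stenosis or stenosis-related hydronephrosis are not enrolled, a case during follow-up is in principle new.

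No objective in 2.2, outcome in 6.2 or row of Table 2 names such an event. Whether it is seen as a harm therefore depends on how a site reads 8.1, and the sentences there point in different directions. At stake is the secondary comparison of serious adverse events and what the DMC is shown. The primary outcome is not affected.

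**Working it through.** **1. The conflicting rules side by side**

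| Question | Rule pointing to inclusion | Rule pointing to exclusion |
|---|---|---|
| Is progression an AE? | 8.1: only disease that fails to progress is excluded | 8.1: signs or symptoms of the studied disease are excluded |
| Is an unplanned admission for endometriosis surgery an SAE? | 8.1: emergency or non-elective procedure admissions, any condition | 8.1: visits for further endometriosis interventions, even if unplanned |
| Is a serious unrelated event recorded and shown to the DMC? | 8.3.3: summarised to the DMC | 8.1 and 8.3.5: recording and summaries framed around related events |

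**2. Four cases traced through the rules**

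- *Acute obstruction with an emergency operation.* It is an SAE under the emergency sentence. It is not one under the further-interventions sentence, nor under the disease-signs exclusion if that is read to cover obstruction. Two sites can each follow the text and disagree.
- *Hydronephrosis found in clinic, with a planned admission for a stent.* The emergency sentence does not apply. The further-interventions sentence keeps it out, and natural history makes a judgement of unrelated likely. It is counted, if at all, as further treatment.
- *Stenosis found incidentally, with no procedure.* The only route is the investigator's judgement that it is medically significant. The disease-signs exclusion and the related-only rule can both close that route.
- *Ureteric stent after surgical injury.* Section 8.2.2 lists stenting among the expected late complications of surgery, so the event can be recorded as an SAE.

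The second and fourth cases involve the same procedure, yet it can count as harm when surgery causes it and not when retained disease does.

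**3. What is caught elsewhere**

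Section 6.2 counts further related surgery, surgery in the medical arm, and discontinuation with reasons. The surgical CRF covers medical-arm women who have surgery (7.3), and the notes of all participants are reviewed at 18 months (7.5). None of the named outcomes separates organ threat from pain. The questionnaires ask about side effects of treatment (section 8).

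**4. Size**

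Inputs: 400 women randomised (10.1), 1:1 allocation (4.8), surgical complications in about 1 in 14 (1.1). The sample size itself reproduces: 2 × (1.96 + 1.2816)² × 22² / 8² = 158.9, so 159 per arm or 318 in total, against 320 stated; 320 / 0.8 = 400. The arms are 400 / 2 = 200.

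Surgical complications if all 200 are operated on: 200 / 14 = 14.3, or 7.1%.

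The protocol gives no progression rate. Let *p* be an assumed 18-month rate in the medical arm and *f* the share that escapes SAE reporting. The number lost is 200 × *p* × *f*. With *f* = 1 (the worst case), and assuming no such events in the surgical arm and no surgical complications in the medical arm:

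| *p* | Women affected | Harms difference if all omitted | If all counted |
|---|---|---|---|
| 0.5% | 1 | 7.1 points | 6.6 |
| 1% | 2 | 7.1 | 6.1 |
| 2% | 4 | 7.1 | 5.1 |
| 3% | 6 | 7.1 | 4.1 |

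If half of the events are reported through the emergency sentence (*f* = 0.5), 0.5 to 3 events are lost. The true *f* is unknown.

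If such events were recorded and none occurred in 200 women, the exact two-sided 95% upper limit would be 1 − 0.025^(1/200) = 1.8%. That limit would apply to clinically detected cases only, with notes reviewed for all 200.

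**The case against.** The strongest reply is that the protocol never says progression is outside the safety data. The AE definition is wide, and the one exclusion about the course of disease removes only disease that stays the same. A seriousness criterion admits anything the investigator finds medically significant. Emergency procedure admissions are SAEs for any condition, all deaths are recorded, and 8.3.3 sends serious unrelated events to the DMC. The consequences of waiting appear as further surgery, crossover and discontinuation with reasons. The CRFs are not shown, so it cannot be said that the indication for surgery goes uncollected.

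Much of this stands, and it rules out several stronger readings:

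- *The AE definition excludes progression.* The text does not say so; it can be read either way.
- *The DMC never sees these events.* Section 8.3.3 contradicts that. The supportable statement is that the DMC may not see them.
- *Obstruction is the main named risk of deferring surgery.* The protocol names it as the situation in which surgery is the only option, and cites a risk to bowel and renal tract when explaining surgical priority. It does not rank the hazards of waiting.
- *The harms comparison is biased in favour of medical management.* This is not shown. The definitions are the same in both arms and also cover women waiting for surgery, and complications of crossover surgery count in the medical arm under intention to treat. Longer exposure to retained disease makes such a bias possible, but its presence and size are unknown.

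The reply does not remove the contradictions. Each protective sentence has an opposing one in 8.1 or 8.3.5, and the emergency sentence does not reach a silent or electively managed case.

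**Conclusion.** The point holds as an inconsistency with a gap behind it. Acute obstruction from endometriosis may or may not be reported as an SAE, depending on which sentence a site follows. New stenosis or hydronephrosis that is silent or managed electively can be left out of the SAE comparison, and no named outcome identifies it.

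The number of events is unknown and probably small: 1 to 6 women in the medical arm at an assumed 0.5% to 3%, of whom only a part would be lost. These rates are assumptions, not figures from the protocol. The events are few but serious, and they bear on a stated secondary objective. This is more than detail left to another document, because the safety rules as fixed here disagree with each other. It should be corrected, though it does not threaten the primary analysis.

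**What to change.** 1. In 8.1, reconcile the sentence on visits for further endometriosis interventions with the sentence on emergency procedure admissions, so that one event has one classification.
2. In 8.1, limit the disease-signs exclusion to pain and other symptoms of endometriosis present before randomisation, so that it no longer conflicts with the exclusion beside it.
3. Align 8.1, 8.3.3 and 8.3.5 on whether serious unrelated events are recorded and summarised to the DMC.
4. State that clinically detected new bowel stenosis or obstruction, new hydronephrosis or hydroureter, and loss of renal function are recorded in both arms from randomisation, whatever the relatedness judgement and whether or not an intervention follows. Use the existing questionnaires, the surgical CRF (indication) and the 18-month case-note review.
5. Report these events by arm to the DMC and beside the SAE and complication outcomes in 2.2 and 6.2.

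The cost is a protocol amendment, a few items on existing forms if they are not already there, and a few more events to process. Ascertainment would still be limited to cases detected in routine care. No change to treatment or imaging is proposed.
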